We have developed 4 low-fidelity prototypes to simulate an intervention component without requiring hard coding. We are calling these "mini interventions" IPs or intervention principles.

We will use a factorial trial to understand each IP prototype's individual and combined feasibility, usability, acceptability, and change in help-seeking intention in an online sample of diverse (racially, ethnically, age, gender identity, sexual orientation) sexual and gender minority youth (SGMY).

2. * Describe the relevant prior experience and gaps in current knowledge

including preliminary data. Provide for the scientific or scholarly background for, rationale for, and significance of the research based on existing literature and how it will add to existing knowledge:

Depression and anxiety are leading contributors to adolescent morbidity, and suicide is the second leading cause of death in this age group. However, fewer than half of affected adolescents access treatment. Rates of depression and suicidality are higher among sexual and gender minority youth (SGMY) and they are less likely than other youth to seek care. Although adolescents with depressive symptoms may be identified in school clinics or primary care settings, identification does not always result in treatment. Adolescents with negative beliefs about diagnosis or treatment and lacking social and parental support are less likely to receive treatment. SGMY at risk of depression are especially difficult to reach as they are less likely to attend preventive primary care visits where routine screening is performed. They may have concerns about confidentiality and disclosing their sexual orientation or gender identity to healthcare or mental health providers, and fear rejection, discrimination, or unsupportive environments. A facilitator of mental health help-seeking, parental support, is often lacking in SGMY who experience more severe depression and suicidality. There is a critical need to develop and test interventions that increase the likelihood of seeking evidence-based treatment among SGMY with depression, anxiety, and suicidality in non-clinical settings.

With SGMY actively immersed online, internet-based interventions are an obvious and promising route to meet SGMY where they are. Yet a recent systematic review found a dearth of evidence-based online mental health interventions for SGMY.

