This intervention trial will use a randomized factorial trial design where each of the 96 participants is randomly assigned to one of 16 combinations of the four study mini-interventions (IPs). There will be 16 possible combinations for the four IPs. For example, one combination will include no IP, and one combination will include all four IPs, and four combinations will include only one of the IPs. The rest of the 10 combinations will include a combination of two or three of the IPs (e.g. IP 1 + 2; IP 1 + 2 + 3; IP 2 + 3; IP 1 + 3, etc.) With n=6 individuals randomly assigned to each of the 16 combinations, this will yield n=48 with a given IP versus n=48 without the given IP (averaging over other combinations of the other three IPs) for the test of each main effect.

- 3. Describe the primary and secondary study endpoints:**

The primary endpoints are feasibility, usability, and acceptability of the IP.

The secondary study endpoint is change in help-seeking intention.

- 4. Provide a description of the following study timelines:**

Duration of an individual subject's active participation:

1 month

Duration anticipated to enroll all subjects:

1 year

Estimated date for the investigator to complete this study (complete primary analyses):

4/30/2024

- 5. List the inclusion criteria:**

Adolescents ages 14-19 will be included if they provide their assent and/or consent if 18 or above; have access to a smartphone; have finished 6th grade; have access to and intellectual and physical ability to use the internet; fit demographic criteria (SGMY); and have symptoms of depression and/or anxiety that are mild or more severe (PHQ-8 and/or GAD-7 = 5 or above)

We will routinely monitor the sample to ATTEMPT to reach close to the following proportions based on recruitment and enrollment flow (e.g. if recruitment and enrollment flow is at a steady rate and we have reached the proportions below we may begin to exclude those being oversampled to obtain balance - because of the pilot nature of the study this may not be possible if recruitment flow is slower than anticipated)

50% ages 14-16 and 50% ages 17-19

50% identify as sexual minority but cisgender and 50% identify as not cisgender

at least 40% identify as a racial or ethnic minority

- 6. List the exclusion criteria:**

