*** Identify the subgroups and provide a justification:**

Children under the age of 14 will not be included in study participation.

The intervention is specifically targeting adolescents in middle adolescence (high school age). This is a time period when they may seek mental health help without parental consent in some states (Pennsylvania) and the interventions will be designed for youth who may be able to seek help with or without parental support.

(Note: the interventions we are developing are not treatment interventions, they are interventions to promote help-seeking for actual mental health treatment in SGMY).

Subgroups will not be explicitly excluded in the beginning but once specific proportions are reached (see inclusion criteria), if the recruitment flow is adequate, we will then change our entry based on the proportion not yet reached. We may not be able to do this due to the pilot nature of this study. We aim to have at least 40% of our sample (38/96 individuals) represent a racial or ethnic minority, so once 60% of the sample (58/96 individuals) is recruited that identifies as not belonging to a minority, new interested participants will then begin to be excluded from then on.

8. Describe the power analysis used and cite your method of statistical analysis.

If a power analysis is not possible, thoroughly justify the sample size required for the study, including appropriate literature citation (alternatively provide page reference in attached protocol):

Participants (N=200) will be enrolled. (N=96 will be given baseline. With groups of n=6 randomly assigned to each of the 16 combinations, this will yield n=48 with a given IP versus n=48 without the given IP (averaging over other combinations of the other three IPs) for the test of each main effect. Based on a two-sample t-test, this will yield 80% power for an effect size of 0.58. For testing any two-IP combination, i.e. yes for the first and second IP (versus no for at least one of those two), this will yield n=24 with a given combination of those two IPs versus n=72 without the given combination of two IP; this yields 80% power to detect an effect size of 0.67.

Similarly, for testing any three-IP combination, this will yield n=12 with a given combination of those two IPs versus n=84 without the given combination of two IP; this yields 80% power to detect an effect size of 0.87. In summary, we have sufficient power for detecting a moderate effect size in each of the above scenarios.

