We will report all baseline characteristics (with counts (%) or mean (SD), median (IQR)) by intervention group, and will follow all reporting guidelines of the CONSORT extension to randomized trials of nonpharmacologic treatment[Boutron 2017], including creating a CONSORT diagram for transparent reporting. The primary analyses for the intervention trial will use an analysis of variance (ANOVA) model[Collins 2014](or equivalently a linear model as defined in Equation 1) with the Likert scale response (1-7, which are expected to be normally distributed) for help-seeking intention as the primary outcome and the assigned treatment factors as the explanatory variables; each $x_j = 1$ if the participant is assigned to the j th IP, and $x_j = 0$ otherwise.

$(1)y = \beta_0 + \beta_1 x_1 + \beta_2 x_2 + \beta_3 x_3 + \beta_4 x_4 + \beta_5 x_1 x_2 + \beta_6 x_1 x_3 + \beta_7 x_1 x_4 + \beta_8 x_2 x_3 + \beta_9 x_2 x_4 + \beta_{10} x_3 x_4 + \beta_{11} x_1 x_2 x_3 + \beta_{12} x_1 x_2 x_4 + \beta_{13} x_1 x_3 x_4 + \beta_{14} x_2 x_3 x_4 + \beta_{15} x_1 x_2 x_3 x_4$ The main effect for the 1st IP, for instance, can then be defined as the contrast testing

$(\beta_1 + \beta_5 + \beta_6 + \beta_7 + \beta_{11} + \beta_{12} + \beta_{13} + \beta_{15}) - (\beta_0 + \beta_2 + \beta_3 + \beta_4 + \beta_8 + \beta_9 + \beta_{10} + \beta_{14}) = 0$, where the first set of 8 coefficients correspond to conditions with $x_1 = 1$, and the second set include $x_1 = 0$. We will also test two- and three-way combinations of the different IPs through similar contrasts. For instance, the test for having both the first and second IP (versus no for at least one of those two, averaging over other IP combinations) will be tested using the following contrast: $(\beta_5 + \beta_{11} + \beta_{12} + \beta_{15}) - (\beta_0 + \beta_1 + \beta_2 + \beta_3 + \beta_4 + \beta_6 + \beta_7 + \beta_8 + \beta_9 + \beta_{10} + \beta_{13} + \beta_{14}) = 0$.

While the linear model and factorial design also allow for testing interactions, e.g. whether the effect of the first IP differs by presence or absence of the second IP, these effects were of less interest for our hypotheses, and will therefore only be considered as exploratory analyses. The other outcome measures and exploratory analyses and can be tested in the same manner with the above linear model. Normality of outcomes will be

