Those individuals who provide consent will be redirected to complete an online survey over RedCAP. Data will be captured on demographics including age, sexual identity, gender identity, race, ethnicity, education, parent/guardian support, homelessness, socioeconomic and social status, transportation access, prior mental health treatment, whether they have a PCP, health insurance status, access to mental health professionals as determined by county and HRSA Health Professional Shortage Area score, and past discriminatory experience by a mental health provider. Mechanistic and outcome survey constructs will at baseline assess: mental health personal and perceived stigma, SGM stigma (internalized homophobia and transphobia), attitudinal barriers toward seeking therapy, antidepressant outcome expectations, expectance of rejection due to SGM, concealment of SGM from others, confidentiality concerns, brief depression/anxiety knowledge, emotional support, help-seeking intention from multiple sources, a single help-seeking intention Likert scale likelihood question (i.e. 'I intend to seek help from a counselor or therapist for my mental health problems' scale 1-795), perceived need, actual help-seeking, depression symptoms (PHQ-8), anxiety symptoms (GAD-7), social isolation (UCLA scale), and perceived health (SF-12). Once the baseline survey is completed, then the participant will be provided with information that the research team will contact them soon with next steps.

Randomization

Once the adolescent completes the baseline survey, RedCAP software will be used to conduct randomization. For those who do not complete the baseline survey, they will not be randomized. The randomization schema will be pre-determined by the study statistician using the RedCAP randomization module. There will be 16 groups to be randomized to with 6 individuals randomized to each group. The mini-interventions or intervention principles (IPs) will be described below.

Intervention

Each individual will be invited to join a private virtual Discord server (<https://discord.com>). They will be asked to create a new Discord account for purposes of participating in the study which does not include any identifiable contact information.

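### The endpoint section and the analysis section name different primary outcomes, and the three endpoints called primary have no analysis that works as written

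*Combined protocol and SAP*

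**What the plan says.** Study Design item 3 sets the ranking: "The primary endpoints are feasibility, usability, and acceptability of the IP", and "The secondary study endpoint is change in help-seeking intention". Study Aims item 1 lists the four outcomes together without ranking them: "individual and combined feasibility, usability, acceptability, and change in help-seeking intention".

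Study Design item 8 describes the primary analyses as an ANOVA, or the equivalent linear model (Equation 1), with the 1-7 Likert response "for help-seeking intention as the primary outcome and the assigned treatment factors as the explanatory variables". Equation 1 contains an intercept and every main effect and interaction of the four IPs, 16 coefficients in all. It has no baseline term, and the response is not defined as a change. Yet the Baseline Survey section includes "a single help-seeking intention Likert scale likelihood question", and the Follow Up Survey section repeats the outcome constructs at 30 days.

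For everything else, item 8 offers one sentence: "The other outcome measures and exploratory analyses and can be tested in the same manner with the above linear model". The Follow Up Survey section says how the three item 3 endpoints are measured, in every group except Group 1, which receives no IP: task completion and time used for feasibility, the System Usability Scale (SUS) for usability, and open-ended questions for acceptability.

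The power paragraph of item 8 describes the main-effect comparison as "averaging over other combinations of the other three IPs) for the test of each main effect" and continues: "Based on a two-sample t-test, this will yield 80% power for an effect size of 0.58". It does not say which outcome this refers to.

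**The concern.** Both statements are current text, and they disagree on which result is the trial's primary result. A null help-seeking finding could be presented as secondary by citing item 3, and a positive one as primary by citing item 8. Each presentation would have support in the plan. The gap between a 30-day score and a change from baseline adds a second choice to the same result.

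The three endpoints that item 3 calls primary are left with a generic sentence. If an analyst follows it, the model cannot be fitted in full, and the effect described in the power paragraph cannot be estimated. The analysis actually used for the declared primary endpoints would then be decided outside the plan.

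**Working it through.** **1. The labels side by side**

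| Outcome | Study Design item 3 | Study Design item 8 |
|---|---|---|
| Feasibility, usability, acceptability | primary | not named |
| Help-seeking intention | secondary, as change | primary, as the 1-7 response |

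**2. The plan's own power figure.** Inputs from item 8: 48 v 48, effect 0.58 in SD units, two-sample t-test. The plan does not state alpha or sidedness; I assume two-sided 0.05, SD 1 and no attrition.
- SE = sqrt(1/48 + 1/48) = 0.204
- Noncentrality = 0.58 / 0.204 = 2.84, with df = 96 - 2 = 94
- Power (noncentral t) = 80.3%

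This reproduces the stated 80%. A one-sided test would give about 88%, so two-sided is the reading that fits. The power arithmetic is sound.

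**3. Equation 1 without Group 1.** There are 16 cells of 6. Dropping the no-IP cell leaves 15 cells and 90 people. The design matrix has rank 16 with all cells and rank 15 without Group 1, for 16 coefficients.

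The averaged effect of IP 1 is the mean of the eight cells with IP 1 minus the mean of the eight cells without it. The no-IP cell mean enters with weight -1/8. No data exist on that cell for these endpoints, so the effect is not estimable. The same holds for the other three IPs.

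**4. The IP 1 contrast as printed in item 8.** With 0/1 coding, the 16 coefficients sum to mean(1,1,1,1), and the eight that do not involve IP 1 sum to mean(0,1,1,1). The first printed set therefore equals mean(1,1,1,1) - mean(0,1,1,1). Subtracting the second set gives

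mean(1,1,1,1) - 2 x mean(0,1,1,1).

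This can be estimated without Group 1, but it is not the averaged IP effect. If every cell mean were 4, it would equal 4 - 8 = -4 rather than 0.

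**5. What reduced models cost on the 15 cells.** SE = sqrt(L'(X'X)^-1 L), where L is the averaged IP effect as the reduced model defines it. Assumptions are 6 per cell, SD 1, two-sided 0.05, no attrition and effect 0.58.

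| Model | Parameters | df | SE | Power at 0.58 | Effect detectable with 80% power |
|---|---|---|---|---|---|
| 48 v 48 as in the plan | 2 | 94 | 0.204 | 80% | 0.58 |
| Main effects only | 5 | 85 | 0.213 | 77% | 0.60 |
| Plus all two-way terms | 11 | 79 | 0.224 | 73% | 0.63 |
| Equation 1 without the four-way term | 15 | 75 | 0.289 | 51% | 0.82 |

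The loss is small only if interactions are assumed absent.

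**6. Per-IP estimates.** Each IP is assigned in 8 cells, 8 x 6 = 48 people. In 7 of those cells, 7 x 6 = 42 people, other IPs are also assigned. The 95% CI half-width for a mean of 48 is 2.01 / sqrt(48) = 0.29 SD.

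**The case against.** The trial describes itself as a pilot, and its measures are not vague. Feasibility is defined by task completion and time used, and usability by a named instrument; both have obvious descriptive summaries. Leaving Group 1 out is natural, because it has no IP to rate. The sentence on other outcomes is permissive, item 8 treats interactions as exploratory, and fitting a reduced model is an ordinary adaptation. Item 8 also allows transformations and generalized linear models. The Research Sites section lists NVivo among the products needed, which points to qualitative handling of the open-ended answers. The grant application and the list of measures are attachments not shown and may say more.

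Most of this stands, and it limits the point. A reader might infer that the three endpoints have no analysis at all. The documents do not support that: the generic sentence could cover them, and descriptive summaries are implied. What is missing in the text provided is an explicit link to the three endpoints, a stated precision and a model that runs. A transformation or another link function does not fill an empty cell, and naming a software tool does not state a method.

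None of it answers the conflict of labels. Pilot status does not settle which outcome is primary when item 8 itself declares one.

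**Conclusion.** The contradiction is real and should be resolved before results are reported. As written, the plan does not identify its primary outcome, nor whether help-seeking intention is analysed as a 30-day score or as a change.

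The second part is narrower. For the three item 3 endpoints, Equation 1 is one cell short, and the averaged IP effect of the power paragraph is not estimable. A main-effects model repairs this for 3 points of power (80% to 77% at 0.58). Keeping interactions costs more: 73% with two-way terms and 51% with three-way terms as well. These figures assume 6 per cell, two-sided 0.05, no attrition, and that 0.58 is meant to apply to such an outcome, which the plan does not say.

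A reader might also infer that the primary outcome was switched after data were seen. The Recruitment Methods section shows that enrollment had begun, but nothing shows that either statement was changed afterwards or that outcome data had been examined. The documents support a contradiction, not a switch.

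**What to change.** 1. Make Study Design items 3 and 8 name the same primary outcome, by a dated amendment that says whether outcome data had been seen. Label the help-seeking model and the power statement to match. State whether the help-seeking response is the 30-day score or the change from baseline.

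2. For feasibility and usability, replace the sentence on other outcomes with an analysis that works without Group 1. Give estimates with 95% CI among the 48 assigned each IP, labelled as describing the IP in combination because 42 of the 48 also receive others. If IPs are compared, use a main-effects model on the 15 measured cells, state that it assumes no interactions, and report the power figures above. Do not use the contrasts as printed in item 8 for this purpose.

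3. Summarise the open-ended acceptability answers qualitatively rather than through Equation 1.

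The cost is wording, one dated amendment and the qualitative summary. The sample does not change and no new data are needed. The one statistical downside is the modest loss of power in the main-effects model and its reliance on no interactions, which should be stated.

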IP 3 Description: Difficulty with garnering parent or guardian support of mental health and LGBTQ status. Finding the words to communicate with their parent, or for themselves regarding names and identities for how they feel. Anticipating dismissal of their concerns and how they can find other supportive adults who can help them navigate communicating with a parent or guardian. Specific resources that they can offer to their parent (i.e. support groups, reading material, professionals) so their parent can receive assistance navigating their child's LGBTQ status instead of them having to educate their parent.

IP 4 Description: Finding affirming professionals. How to identify whether mental health professionals are competent in working with LGBTQ+ youth. Reviewing resources that help to identify mental health friendly spaces online. Reviewing what questions they can ask of a provider or a healthcare setting to know whether they would be affirming. What the law says about conversion therapy.

The research team will moderate all online discussions and provide feedback to individuals to guide them to factual information that can help answer their questions. Individuals will be prompted by text message each week to remind them to contribute to the Discord community.

Follow Up Survey (1 month)

All randomized individuals will receive a follow-up survey 30 days after they complete the baseline survey. Mechanistic and outcome survey constructs will be repeated in this survey. Additionally, in all but Group 1, we will measure Feasibility (i.e. proportion of IP tasks completed, length of time IP used); Usability utilizing the System Usability Scale (SUS); and Acceptability using open-ended questions regarding whether each IP group was helpful, affirming of SGM status, if timing and amount of content were appropriate, if privacy and confidentiality were maintained, and if they had any negative consequences of participation (e.g. parent questioning them).

Participants will be compensated for each research activity as described in compensation.

2. Upload a copy of all materials used to collect data about subjects: (Attach all surveys, interview/focus group scripts, and data collection forms except for case report forms, SCID or KSADS):

Document	Category	Date Modified	Document History
View SMASI (Modified, using items 14-16) (1.0)	Data Collection	6/22/2023	History
View Global Unique Identifier Information.docx(0.01)	Data Collection	2/24/2023	History

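### The help-seeking model leaves out the baseline score of its own outcome, which costs precision and leaves open whether the outcome is the follow-up score or the change.

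*Combined protocol and SAP*

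**What the plan says.** The Study Aims (item 1) name as targets the "individual and combined feasibility, usability, acceptability, and change in help-seeking intention" of each prototype. Study Design, item 3, agrees: "The secondary study endpoint is change in help-seeking intention".

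The analysis in Study Design, item 8, is an ANOVA or linear model "with the Likert scale response (1-7, which are expected to be normally distributed) for help-seeking intention as the primary outcome", with "the assigned treatment factors as the explanatory variables". Equation 1 has an intercept and 15 terms built from the four assignment indicators. It has no baseline term, and y has no time point. Item 8 mentions no covariate adjustment; baseline characteristics are to be reported descriptively by group.

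The baseline score exists. Under Research Activities, the Baseline Survey includes "a single help-seeking intention Likert scale likelihood question" scored 1 to 7. The Randomization paragraph adds: "For those who do not complete the baseline survey, they will not be randomized". The Follow Up Survey paragraph states "All randomized individuals will receive a follow-up survey 30 days after they complete the baseline survey" and "Mechanistic and outcome survey constructs will be repeated in this survey".

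**The concern.** Two things are wrong, and one change repairs both.

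First, a person's intention to seek help before randomisation is likely to predict the same person's answer 30 days later. Leaving it out puts that predictable variation into the error term of every contrast. The trial randomises 96 people to 16 cells of 6, and its three-IP contrasts rest on 12 versus 84, so precision is scarce.

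Second, a change score on a 1-7 item runs from -6 to +6, so the modelled response is not the stated endpoint. Two analysts could follow the plan in good faith, one analysing the 30-day score and the other the raw change. Their analyses would have different power and could reach different conclusions.

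**Working it through.** **Inputs.** From Study Design, item 8: 48 versus 48 at effect size 0.58, 24 versus 72 at 0.67 and 12 versus 84 at 0.87, each at 80% power, from a two-sample t-test. Assumptions: two-sided alpha 0.05 (the plan states none, but this reproduces its figures, whereas one-sided 0.05 gives about 88%); baseline to follow-up correlation r from 0 to 0.7; equal SDs at both times; all 96 followed up; and contrasts that compare means as item 8 intends.

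**Plan's own figures.** Power comes from the noncentral t with noncentrality d / sqrt(v(1/n1 + 1/n2)), where v = 1 for an unadjusted follow-up score.

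- 48 versus 48: sqrt(1/48 + 1/48) = 0.204 and 0.58/0.204 = 2.84, giving 80.3% (80.2% on the 80 residual degrees of freedom of Equation 1, 96 - 16).
- 24 versus 72 at 0.67: 80.3%.
- 12 versus 84 at 0.87: 79.7%.

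All three reproduce.

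**Alternatives.** Baseline as covariate: v = 1 - r², on 79 degrees of freedom. Raw change without a covariate: v = 2(1 - r), on 80. For example, at r = 0.5 the adjusted v is 0.75, the noncentrality is 2.84/sqrt(0.75) = 3.28 and power is 90.0%. For raw change at r = 0.3, v is 1.4, the noncentrality is 2.84/sqrt(1.4) = 2.40 and power is 66.0%.

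| r | Adjusted: power at 0.58, 48 v 48 | Adjusted: detectable effect, 48 v 48 | 24 v 72 | 12 v 84 | Raw change: power at 0.58 | Raw change: detectable effect, 48 v 48 |
|---|---|---|---|---|---|---|
| 0 | 80.1% | 0.579 | 0.669 | 0.875 | 51.0% | 0.819 |
| 0.2 | 81.7% | 0.567 | 0.655 | 0.858 | 60.2% | 0.732 |
| 0.3 | 83.7% | 0.552 | 0.638 | 0.835 | 66.0% | 0.685 |
| 0.5 | 90.0% | 0.501 | 0.579 | 0.758 | 80.2% | 0.579 |
| 0.6 | 93.9% | 0.463 | 0.535 | 0.700 | 88.1% | 0.518 |
| 0.7 | 97.6% | 0.413 | 0.477 | 0.625 | 95.2% | 0.448 |

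Detectable effects are at 80% power.

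**Reading the table.** Since 1 - r² = (1 - r)(1 + r), the adjusted variance never exceeds that of the raw follow-up score (1) or of raw change (2(1 - r)). Raw change is noisier than the follow-up score whenever 2(1 - r) > 1, that is, r < 0.5. At r = 0.5 the standard error falls by 13.4%, and 96/0.75 = 128, so adjustment is worth about 32 participants.

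**Cost of estimating the slope.** Chance baseline imbalance inflates the adjusted variance by about 1 + 1/78 = 1.013 on average, which the table ignores. Including it changes power from 80.1% to 79.6% at r = 0 and from 90.0% to 89.6% at r = 0.5. Variance breaks even where (1 - r²)(79/78) = 1, so r² = 1/79 and r is about 0.11.

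**Follow-up or change.** With baseline Y0 in the model, regressing Y1 - Y0 on treatment and Y0 gives the same treatment coefficients as regressing Y1; only the slope on Y0 shifts by 1. Adjustment therefore makes the choice immaterial.

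**The case against.** The strongest reply is that this is an efficiency choice. An unadjusted randomised comparison is valid, its power was calculated for that test, and the calculation is right. That stands: the trial is not short of its own claim because the covariate is missing.

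The gain depends on an r that the documents do not give. That also stands: it is modest at 0.3, and at r near zero there is nothing to gain. The 66% for raw change belongs to the low end of the range and to an analysis that item 8 does not clearly specify; at r = 0.7 raw change reaches 95.2%.

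Chance imbalance is not a second defect. The intended contrasts average over cells, so the SD of a baseline difference is 0.204 baseline SDs for 48 versus 48, and it contributes r × 0.204, or 0.06 to 0.14 SD for r of 0.3 to 0.7. The t-test's standard error already carries that variation. Removing its linear part is the precision gain itself and should not be counted twice.

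Nor does the covariate help the feasibility, usability and acceptability endpoints, which are measured only at follow-up. Finally, the printed main-effect contrast subtracts the intercept, so adding an uncentred baseline score would change what it tests. These points limit the size of the benefit and show what the fix must include. They do not supply a baseline term or reconcile the two descriptions of the outcome.

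**Conclusion.** The concern holds. Equation 1 omits a pre-randomisation measure of its own outcome, and the outcome it models does not match the stated change endpoint.

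Over an assumed r of 0.3 to 0.7, adjustment raises main-effect power at 0.58 from 80% to between 84% and 98%, and lowers the detectable effect from 0.58 to between 0.55 and 0.41. For three-IP contrasts, the detectable effect falls from 0.87 to 0.76 at r = 0.5. If r is near zero, adjustment costs about half a percentage point of power. The omission is certain; the size of the gain is not.

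The figures assume a normal linear model and complete follow-up. The plan states no dropout allowance; at an assumed 20% loss, main-effect power is 70.6% unadjusted and 82.3% adjusted at r = 0.5. This is a change the plan should make, not a fault that invalidates it.

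**What to change.** 1. Define y as the 30-day score on the single 1-7 intention item, and make the Study Aims and Study Design items 3 and 8 agree. Item 3 ranks the endpoint as secondary and item 8 calls it primary; settle that in the same edit.
2. Add the baseline score of that item to Equation 1, centred at its overall mean.
3. Write each contrast as a difference in adjusted cell means, so that the intercept and the baseline term cancel. Under the plan's 0/1 coding, the IP 1 main effect is β1 + ½(β5 + β6 + β7) + ¼(β11 + β12 + β13) + ⅛β15, which averages over the eight settings of the other IPs.
4. State a rule for a missing baseline item, since participants may skip items (Waiver/Alteration of Consent, item 2). Imputing the overall baseline mean without regard to assignment would do.
5. Keep the covariate if a transformation or another generalized linear model is used, and treat other outcomes measured at both times in the same way.
6. If outcome data have already been examined, report the adjusted model as specified afterwards, beside the unadjusted one.

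The cost is a short edit to item 8 and one of 80 residual degrees of freedom. No new data are needed.
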